2.3.2 Microbial-directed Passive Immunotherapies

For infections with a clear natural immune correlate of antibody-dependent protection and/or eradication, it is possible to quickly develop medical products containing high titers of such antibodies, or products with similar properties. These are "passive" immunotherapies as their intrinsic activity does not rely on the patient's immune system.

There are two principal approaches for such medical products.

The first approach is to develop a product entirely in the laboratory such as monoclonal antibodies, or other molecules serving a function similar to antibodies. The clones are retrieved from convalescent persons, and among these clones, those expressing high titers of antibodies with effective neutralizing abilities are identified and propagated. The Fc section of the antibody may be genetically modified in order to reduce the natural Fc function or to extend

Version 1.0, 11th November 2022

US IND# 162149

the half-life of the monoclonal antibody [30]. There are examples of other technologies able to induce neutralization similar to that of antibodies, for example the DARPin technology [31].

The alternative approach to developing microbial-directed immunotherapies is to retrieve antibodies from convalescent plasma using plasmapheresis. By using vaccinated donors, titers of the harvested neutralizing antibodies may increase relative to those retrieved from convalescent persons. The product from plasmapheresis may undergo subsequent refinement and purification. Such products are collectively called "hyperimmune intravenous immunoglobulin" (hlVIG) [32-35].

Trials investigating microbial-directed immunotherapies may evaluate the efficacy and safety of a specific immunotherapy, or address strategic questions related to dosing and timing for initiation of use.

2.3.3 Agents Affecting Host-pathways Involved in Organ Injury

Host-response therapies aim to improve clinical outcomes by modulating the body's response to infection. These therapies may modulate the host immune response (immunomodulatory therapies) or other host pathways, such as the coagulation pathway and renin-angiotensin aldosterone pathway. Depending on the respiratory pathogen under study, the inflammatory response may be exclusively helpful to the host or may adversely contribute to the progression of the disease. As such, the study of immunomodulatory agents will be central to STRIVE. Most immunomodulatory agents are likely to be repurposed drugs already in use for the treatment of autoimmune diseases. Examples of immunomodulatory therapies that may be studied as treatments for severe respiratory infections include corticosteroids [7, 36, 37], JAK-inhibitors, and monoclonal antibodies [6] and other therapies that inhibit specific inflammatory pathways, cytokines, or chemokines, such as IL-6 [38-40], TNF-α, IL-1β, CXCL8, IL-1β, T2-mediated inflammation, IL-5 and/or its receptor, IL-4, IL-13, and IL-33.

Host-response therapies may also have specific tissue protective properties, either by protecting tissues from injury caused by the pathogen or the resulting immune response, or by accelerating the formation of healthy tissue (e.g., agents focused on stem cell function).

STRIVE trials evaluating host-response therapies may assess the efficacy and safety of a specific agent compared with placebo or compared with other host-response agents. Strategic questions related to timing (when in the course of infection to initiate), intensity (use of one or several agents together), or duration of use may also be evaluated.

2.3.4 Agents for Treatment of Patients with Critical Illness

Some patients hospitalized with a respiratory pathogen may experience extended critical illness, despite the use of best-practice treatment. Although the patient population is relatively small, the resources used for their care and the mortality risk are extensive. Despite this, the evidence guiding their care is limited.

In many such patients, the causative respiratory pathogen may no longer replicate, but tissue injury is extensive and requires prolonged organ support. For some, there is evidence of intense immunosuppression allowing for reactivation of latent infections with various herpes

Version 1.0, 11th November 2022

US IND# 162149

viruses, including Cytomegalovirus. The clinical phenotype of such patients may overlap across infections with different respiratory pathogens.

Interventions to be evaluated may be derived from the host-response therapies described above, organ supportive care strategies, or therapies for superimposed infection complicating the initial disease.

3 Risk/Benefit Assessment

3.1 Known Potential Risks

Potential risks of participating in trials within this platform are those associated with the interventions under study, which are described in trial-specific appendices. Other risks include those from having blood drawn and intravenous (IV) catheterization (if needed in a particular trial) and breach of confidentiality.

3.1.1 Risks of Drawing Blood and IV Catheterization

Drawing blood may cause transient discomfort and fainting. Fainting is usually transient and managed by having the participant lie down and elevate his/her legs. Bruising at the blood collection sites may occur but can be prevented or lessened by applying pressure to the blood draw site for a few minutes after the blood is taken. IV catheterization may cause insertion site pain, phlebitis, hematoma formation, and infusate extravasation; less frequent but significant complications include bloodstream and local infections. The use of aseptic (sterile) technique will make infection at the site of blood draw or at catheterization less likely.

3.1.2 Risks of Anaphylaxis and Fluid Overload due to Study Treatments

Administration of drugs may cause allergic reaction, which in its most severe form is anaphylaxis. The risks of allergic reaction will be minimized by studying treatments that have evidence of acceptable tolerability without demonstrating a significant risk of allergic reaction, and by administering the first dose of each study drug while the patient is hospitalized in a monitored setting.

For study drugs administered intravenously, the volume of fluid infused may exacerbate preexisting chronic heart failure (CHF). The overall clinical picture of the targeted patient population will be evaluated in determining acceptability of the intervention with regards to this risk.

For antibody treatments studied on the platform, there is a theoretical risk that antibody infusion may worsen the disease course via antibody-dependent enhancement (ADE). ADE occurs if specific antibodies against a virus increase rather than decrease viral replication and hence worsen the disease course. ADE has been observed most clearly in the context of Dengue fever [41].

Host-response therapies may potentially dampen innate and adapted host immune responses, rendering the patient at excess risk of prolonged viral replication and complicating infections.

Clinical manifestations possibly caused by ADE or host-response therapies will be captured in trials evaluating such interventions as appropriate, and their occurrence reviewed by the trial DSMB while the trials unfold.

3.1.3 Risks to Privacy

Participants will be asked to provide personal health information (PHI). All attempts will be made to keep this PHI confidential within the limits of the law. However, there is a chance that unauthorized persons will see the participant's PHI. All source records including electronic data will be stored in secured systems in accordance with institutional policies and government regulations.

All study data that leave the site (including any electronic transmission of data) will be identified only by a coded number that is linked to a participant through a code key maintained at the clinical site. Names or readily identifying information will not be released. Electronic files will be password protected.

Only people who are involved in the conduct, oversight, monitoring, or auditing of this trial will be allowed access to the PHI that is collected. Any publication from trials within STRIVE will not use information that identifies study participants. Organizations that may inspect and/or copy research records maintained at the participating site for quality assurance and data analysis include groups such as the study monitor, and other authorized representatives of the institutional review board (IRB), NIH, and applicable regulatory agencies (e.g., Food and Drug Administration).

3.1.4 Early Phase Development

In the assessment of agents early in the development pathway for which there is only safety data derived from small sample size Phase 1 or 2 trials, there is the potential for participants to be at increased risk due to both foreseeable and unpredictable side effects or drug-drug interactions. Where this is the case, the limited data sets available will be acknowledged in the patient information material and as stated above the trial-specific appendix will have protocol-appropriate adverse event reporting, a plan for staged assessment of the agent by disease severity strata and more intensive safety monitoring. Where drug-drug interactions are known or foreseeable, the trial-specific appendix and Protocol Instructions Manual (PIM) will specify how these will be managed (e.g., co-administration of a drug with the study treatment is prohibited, or the dose of a drug is modified).

3.1.5 Sequential and Co-enrollment

We intend to co-enroll or sequentially enroll patients in clinical trials should the participant fail to improve, or if the clinical picture suggests additional interventions are justified, when such co-enrollment may be appropriate. Particularly with investigational agents in early development there is the potential for unforeseen drug interactions or additive toxicities. The trial-specific appendix will include appropriate adverse event reporting, a plan for staged assessment of the agent by disease severity strata, and more intensive safety monitoring by the DSMB.

3.2 Known Potential Benefits

While each trial conducted on this platform will be conducted to test a hypothesis that an intervention or strategy will benefit patients, the interventions or strategies studied may or may not benefit any individual who participates in one of the trials. There is an anticipated benefit to

US IND# 162149

society from a patient's participation in STRIVE trials from insights gained about the interventions under study as well as the natural history of severe respiratory infections.

4 Outcomes

This section describes three key outcomes (also referred to as endpoints) that will be used in most STRIVE trials. Where feasible, all 3 outcomes listed in this section will be ascertained for STRIVE trials. This will permit secondary analyses across trials to be carried out. We anticipate that most trials will select one of the 3 outcomes described as the primary outcome. Where that is not desirable because of the nature of the intervention and/or the target population, the primary outcome may be described in detail in the trial-specific appendix. Additional secondary and safety outcomes not listed in the master protocol may also be outlined in each trial-specific appendix.

4.1 Primary Outcome

Because this master protocol includes a spectrum of potential respiratory pathogens, at different stages of disease, and a broad scope of potential interventions, a flexible and pragmatic approach to the selection of the primary outcome for each trial is provided. The general principles are that the primary outcome should be patient-centered, acceptable to regulators for registration trials, interpretable to end users including guideline committees and front-line clinicians, easily and reliably ascertainable across hundreds of clinical sites across the globe, and appropriately efficient in terms of sample size required to complete a trial and data collection required.

Three examples of primary outcomes meeting these criteria are presented below:

- 1) All-cause mortality
- 2) Time to sustained recovery
- 3) Clinical Recovery Scale (CRS)

These outcomes are defined below. The follow-up duration during which these outcomes are ascertained will typically be *60 days* to optimize the potential to rapidly identify clinically important differences that are related to the acute presentation and potentially modifiable for the intervention being evaluated, while balancing timeliness and burden of data collection requirements. For circumstances in which later complications related to the intervention or patient population may be more likely, a longer follow-up duration (typically 90 days) for efficacy and/or safety outcomes may be considered by individual trials with compelling scientific justification. Similarly, for circumstances when more rapid ascertainment of the primary outcome is desired (e.g., emerging infections), a shorter follow-up duration (e.g., 28 days) may be considered.

4.1.1 Rationale for Primary Outcome

The primary outcome is intended to identify efficacy among the interventions in a STRIVE trial.

Generally, an individual trial will select one of these potential outcomes based on trial-specific considerations such as the pathogenesis of the infection, severity of illness, and mechanism of

US IND# 162149

the intervention. Trials in populations that have a high anticipated mortality during follow-up (e.g., >20% with usual care) should strongly consider all-cause mortality as the primary outcome (see Section 6.4.1). When all-cause mortality is selected as the primary outcome, time to sustained recovery and the CRS (see Section 4.1.4) will be secondary outcomes.

For trials in populations with relatively lower anticipated mortality, outcomes that incorporate the speed and quality of recovery among survivors (i.e., time to sustained recovery or the CRS), in combination with mortality being classified as the worst outcome in these composite outcomes, will typically be prioritized to optimize efficiency and patient-centeredness. In these cases, all-cause mortality will be an important secondary, and possibly in some trials a coprimary outcome.

4.1.2 All-cause Mortality

All-cause mortality will be assessed through the selected follow-up duration, typically Day 60. Near-complete ascertainment of all-cause mortality is critical, regardless of which primary outcome is selected. Therefore, substantial attempts will be made to determine vital status through the end of follow-up by a combined approach of follow-up visits with the participant or proxy, chart review, and review of other available information sources.

4.1.3 Time to Sustained Recovery

Time to sustained recovery is defined as being discharged from the index hospitalization, followed by being alive and *home* for 14 consecutive days prior to the end of follow-up [42-45]. The primary advantage of time to sustained recovery over the CRS is the ability to ascertain the primary outcome for most participants prior to the end of follow-up.

Home is defined as the level of residence or facility where the participant was residing prior to hospital admission leading to enrollment in this protocol.

Residence or facility groupings to define home are: 1) **Independent/community dwelling** with or without help, including house, apartment, undomiciled/homeless, shelter, or hotel; 2) **Residential care facility** (e.g., assisted living facility, group home, other non-medical institutional setting); 3) **Other healthcare facility** (e.g., skilled nursing facility, acute rehab facility); and 4) **Long-term acute care hospital** (hospital aimed at providing intensive, longer term acute care services, often for more than 28 days).

Lower (less intensive) level of residence or facility will also be considered as home. By definition, "home" cannot be a "short-term acute care" facility. Participants previously affiliated with a "long-term acute care" hospital recover when they return to the same or lower level of care.

Readmission from "home" may occur and if this occurs within 14 days of the first discharge to "home", then the primary outcome will not be reached until such time as the participant has been "home" for 14 consecutive days.

Participants residing in a facility solely for public health or quarantine purposes will be considered as residing in the lowest level of required residence had these public health measures not been instituted.

Version 1.0, 11th November 2022

US IND# 162149

An alternative to the original definition of time to sustained recovery is to require a participant to be alive, home, and not receiving new supplemental oxygen (as defined in Section 4.1.4) for 14 consecutive days to achieve the primary outcome.

For this endpoint the focus is on comparing the cumulative incidence of sustained recovery for the 2 groups and death is considered a competing risk, effectively being counted as not recovered. Because death is not directly considered in this outcome, death and the CRS-60 outcomes will always be important secondary outcomes if this outcome is primary.

4.1.4 Clinical Recovery Scale

The *Clinical Recovery Scale* (CRS) is an ordinal ranked outcome that includes the concepts of mortality, duration of hospitalization, duration of being at home but not fully recovered, and duration fully recovered. It may include up to 63 categories, with a description of each level detailed in Table 4.1. At the end of the follow-up period, each patient is classified into one of the CRS levels. By default, trials in STRIVE will use a 60-day follow-up; the CRS evaluated at 60 days is termed *CRS-60*.

Ordinal outcomes, and corresponding summary measures to compare groups such as ratios of the odds of being in a better category if having received the active treatment (vs control) have been used extensively as a primary outcome in relation to acute infections. The CRS incorporates into one outcome both risk of progression to serious disease including death as well as the ability to recovery. To interpret the findings, summary statistics for median days fully recovered, the proportion not recovered (including those who died), by treatment arm, will be provided.

For the CRS, the definition of "home" is the same as used for time to sustained recovery.

The definition of what constitutes "recovery" after reaching home will be detailed in each trial; an example of "recovery" is being alive and at home without need of new supplementary oxygen.

The "last-off" method for assessing full recovery will be used, as has been customary in the use of similar ordinal outcomes [46]. According to the "last-off" method, periods of being at home that are followed by hospital re-admission, change from home to a higher level of care, or receipt of an intervention at home that defines the patient as not fully recovered (e.g., supplemental oxygen) will *not be counted* toward the number of days in recovery. In other words, only days between the last time the patient entered a fully recovered state (i.e., returned home, and fully (e.g., free of new supplemental oxygen) recovered), and the end of follow-up are counted as days of full recovery.

Table 4.1: Clinical Recovery Scale for a Trial with 60 Days of Follow-up (*CRS-60*) and Its Categories

CRS-60 category	Description
60-1 ¹	Days to recovery (i.e., at home and fully recovered)
0	Alive, at home but not fully recovered ¹ by Day 60
-1	Still hospitalized by Day 60
-2	Dead

¹ Categories 1 to 60 depict the days fully recovered during the 60 days of follow-up (i.e., recovered for 60 days and down to 1 day). Individual trials may "bin" these categories, e.g., recovered for < 20, 21-30, 31-40, 41-45, 46-50, 51-55, and > 55 days (7 categories to classify the duration of recovery in addition to the first 3 categories representing death, still hospitalized at Day 60, and not recovered at Day 60).

If the CRS is ascertained at a different follow-up time than 60 days, the rationale for using a different timepoint will be explained in the trial-specific appendix. Options include ascertainment of the CRS at 28 days (*CRS-28*) and 90 days (*CRS-90*). For example, with *CRS-28*, the maximal number of days at home and fully recovered is 28 (and not 60 as in *CRS-60*). The CRS outcome requires full follow-up time to ascertain the final outcome status for individual participants, though earlier assessments may be used for interim analysis.

4.2 Secondary Outcomes

Primary outcomes outlined above not designated as the primary outcome for a specific trial will be assessed as important secondary outcomes. In addition, several secondary efficacy outcomes will be assessed for all participants.

4.2.1 Rationale for Secondary Outcomes

The main secondary outcomes for the STRIVE platform are constituents of or related to the potential primary outcomes. In addition, the ordinal outcome described in bullet point 5 below, extrapulmonary organ failure, and secondary infections are important to understand the full range of physiological recovery. The rationale for the safety outcomes collected is presented in Section 10. If additional secondary outcomes are to be added, refined, or not used for specific trials, these outcomes will be specified in the trial-specific appendix.

4.2.2 Secondary Efficacy Outcomes

- 1. Time to discharge from the initial hospitalization
- 2. Days alive and home through the end of follow-up, using the "last off" method as described in Section 4.1.4
- 3. Proportion of participants who are alive and at home, and proportion of participants who are alive, at home and free of new supplemental oxygen at days 14, 28, and at end of follow-up (typically Day 60) if home oxygen use is assessed in a given trial.

² An example of a state where the patient is alive at home but not fully recovered is the need for continuous supplementary oxygen. The exact definition for not being fully recovered will be outlined in each trial-specific appendix.

Version 1.0, 11th November 2022 US IND# 162149

- 4. CRS-28
- 5. Ordinal outcome (categories defined below), on Days 1-7, 14, and 28:
 - 1. Can independently undertake usual activities with minimal or no symptoms
 - 2. Symptomatic and currently unable to independently undertake usual activities but no need of supplemental oxygen (or not above premorbid requirements)
 - 3. Supplemental oxygen <4 liters/min (or <4 liters/min above premorbid requirements)
 - 4. Supplemental oxygen ≥4 liters/min (or ≥4 liters/min above premorbid requirements, but not high-flow oxygen)
 - 5. Non-invasive ventilation or high-flow oxygen
 - 6. Invasive ventilation, extracorporeal membrane oxygenation (ECMO), mechanical circulatory support, or new receipt of renal replacement therapy
 - 7. Death
 - 6. Health-related quality of life by EuroQol (EQ-5D-5L) at the end of follow-up [47]

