11.3.2.1 Early Futility Assessment

In some cases, an early futility assessment may be specified using an intermediary futility outcome. For example, in a trial where the primary outcome is an ordinal scale assessed at Day 60 (e.g., *CRS-60*), an early futility assessment could be based on time to hospital discharge, or on the 7-category ordinal outcome assessed at Day 14. This might be warranted when there is an acceptable intermediate outcome and many competing agents in the platform combined with the need to quickly identify and concentrate resources on the most promising agent(s), or when preliminary data supporting activity of the investigational agent in the trial population is lacking and thus establishing such activity is warranted to justify further resource intensive evaluation based on the primary outcome. Rationale and details regarding such an approach will be prespecified in the trial-specific appendix.

12 Protection of Human Subjects and Other Ethical Considerations

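### The 7-category ordinal outcome exempts premorbid oxygen and dialysis but not premorbid ventilation, so long-term home ventilation users are capped or scored inconsistently (minor).

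*Protocol*

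**What the plan says.** Protocol 4.2.2 item 5 defines a seven-category scale for Days 1-7, 14 and 28, running from 1 (best) to 7 (death).

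- Category 1 is purely functional: "Can independently undertake usual activities with minimal or no symptoms".
- Category 2 covers participants who are symptomatic and limited but have "no need of supplemental oxygen (or not above premorbid requirements").
- Category 3 is "Supplemental oxygen <4 liters/min (or <4 liters/min above premorbid requirements"), and category 4 ends "liters/min above premorbid requirements, but not high-flow oxygen".
- Category 5 is "Non-invasive ventilation or high-flow oxygen".
- Category 6 is "Invasive ventilation, extracorporeal membrane oxygenation (ECMO), mechanical circulatory support, or new receipt of renal replacement therapy".

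Section 11.2 analyses the scale with proportional odds models stratified by disease severity and site. Section 11.3.2.1 lists possible intermediate outcomes for early futility: time to discharge, "or on the 7-category ordinal outcome assessed at Day 14". Section 4.2.1 lets a trial-specific appendix refine or drop secondary outcomes. The platform exclusions in 7.2 do not mention long-term ventilation.

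**The concern.** Three of the lower categories and one component of category 6 discount support that the participant already had before the illness. The ventilation and circulatory-support items do not, and no reason is given. A participant on usual nightly non-invasive ventilation at home, active and well at Day 14, can therefore be placed in category 5, below an inpatient on conventional oxygen at 4 liters/min or more.

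Two consequences follow. Where sites apply the categories in order of severity, improvement in these participants beyond category 5 or 6 is invisible and the odds ratio is pulled toward 1. Where sites score by activity, the same clinical state is recorded as 1, and the data depend on local interpretation. Both matter more if a trial uses the Day 14 scale for futility, because dilution makes an effective agent look less promising.

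**Working it through.** **Step 1: the text, item by item**

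| Component | Category | Discounts premorbid support? |
|---|---|---|
| Oxygen, none or below 4 liters/min | 2, 3 | Yes |
| Oxygen, 4 liters/min or more | 4 | Yes |
| Non-invasive ventilation, high-flow oxygen | 5 | No |
| Invasive ventilation, mechanical circulatory support | 6 | No |
| Renal replacement | 6 | Yes (new receipt only) |

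No other section supplies the missing qualifier for this scale. The respiratory-failure safety outcome in 4.2.3 counts only support above the enrollment level, but that rule is not carried over. Section 4.1.3 says that participants from a long-term acute care hospital "recover when they return to the same or lower level of care"; this also refers to premorbid status, but concerns residence.

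**Step 2: what score results**

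Take a participant on usual home non-invasive ventilation, active, with minimal symptoms. Category 1 fits, because it does not mention respiratory support. Category 5 also fits. The protocol has no tie-breaking rule. Severity order gives 5; functional reading gives 1. With premorbid invasive ventilation the severity-ordered score is 6. A participant back on premorbid low-flow oxygen can score 2 or better, and premorbid dialysis alone does not lead to category 6.

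**Step 3: illustrative size**

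The protocol states no power, prevalence or category distribution for this outcome, so there is no figure to reproduce (Tables 6.3 and 6.4 concern CRS-60). All inputs below are assumptions: true odds ratio 1.35, two-sided 5% test, 1:1 allocation, no stratification, and these control-arm proportions for categories 1 to 7:

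- A, recovering (70% in categories 1-2): 0.40, 0.30, 0.09, 0.05, 0.05, 0.05, 0.06
- B, recovering (78%): 0.55, 0.23, 0.05, 0.03, 0.02, 0.04, 0.08
- C, sicker (22%): 0.08, 0.14, 0.13, 0.13, 0.18, 0.20, 0.14

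The treated arm follows from multiplying each cumulative odds by 1.35. For A the first is 0.40/0.60 × 1.35 = 0.90, giving 0.474 in category 1.

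The total size for 80% power is N = 12(1.960 + 0.842)² / [(ln OR)² (1 − Σp̄³)], where p̄ are the pooled proportions. For A: 12 × 7.849 / (0.3001² × 0.8906) = 1174.

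Next, move a fraction f of those in categories 1-4 to category 5 in both arms, refit the proportional odds model to the resulting proportions (giving OR′), and recompute power = Φ(ln OR′ × √[N(1 − Σp̄′³)/12] − 1.960). For A at f = 5%: OR′ = 1.318 and 1 − Σp̄′³ = 0.9055, so 0.2764 × √(1174 × 0.9055/12) = 2.602, and Φ(0.642) = 0.740.

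| f | A: power, OR′ | B: power, OR′ | C: power, OR′ |
|---|---|---|---|
| 1% | 78.8%, 1.343 | 78.7%, 1.342 | 79.7%, 1.348 |
| 3% | 76.4%, 1.331 | 76.1%, 1.327 | 78.9%, 1.345 |
| 5% | 74.0%, 1.318 | 73.4%, 1.312 | 78.2%, 1.341 |
| 8% | 70.2%, 1.301 | 69.3%, 1.293 | 77.2%, 1.337 |

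The loss is largest where most participants would otherwise be in categories 1-2. It is small where many are already in category 5 or worse, a pattern more likely on early assessment days.

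**The case against.** The strongest reply is that little in the plan depends on this. The scale is a secondary outcome with no stated power. Appendices may refine it, and they supersede the master protocol. No primary outcome, sample size or harm boundary uses it. Randomization makes the misclassification non-differential in expectation. The subgroup is probably small, and at 1% affected the loss is about one point. All of this stands and sets the severity. It does not repair the default wording, since 4.2 applies the secondary efficacy outcomes to all participants and each trial inherits the definition unless its appendix changes it.

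Three stronger readings are tempting and are not supported:

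- *These participants are fixed near the worst end whatever the treatment does.* That needs a rule that the worst fitting category wins. The protocol states none, and a recovered user also fits category 1. Even on the severity-ordered reading, 5 or 6 is only the best attainable score; worsening still registers.
- *The scale contradicts 4.1.3.* Sustained recovery is defined by residence, and the ordinal scale by function and organ support. The same person can be recovered on one and supported on the other without contradiction. Section 4.1.3 shows only that premorbid status is handled differently there.
- *The flaw drives a futility decision.* Section 11.3.2.1 offers the Day 14 scale as one option, with rationale and details left to the trial appendix. No such decision is fixed here.

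**Conclusion.** The asymmetry is real and is on the face of 4.2.2. For a participant at a premorbid level of home ventilation, the score is capped at 5 or 6 on a severity-ordered reading and ambiguous otherwise. The expected result is some dilution toward no effect plus inconsistent scoring between sites, without directional bias.

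The size cannot be derived from the documents. Under the assumptions shown, the loss of power is about 1 point at 1% affected and about 4 to 7 points at 3 to 5% in mostly recovering populations. In the sicker one it is about 0.3 to 2 points over the same 1 to 5% range. Other plausible distributions, or counting the affected share over all participants, give somewhat smaller losses (about 3 to 5 points at 3 to 5%). Severity is minor: a definition worth correcting before trials inherit it, with more reason to do so where Day 14 is chosen for futility.

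**What to change.** In 4.2.2 item 5:

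1. Add *new or above premorbid requirements* to non-invasive ventilation and high-flow oxygen in category 5, and to invasive ventilation and mechanical circulatory support in category 6.
2. State that, after this exemption, the worst applicable category is assigned. Participants at their premorbid level of support are then scored on the remaining criteria.
3. Add premorbid ventilatory and circulatory support, with type and usual pattern of use, to the baseline history in 9.3.1 and Appendix A, which do not list it specifically. The instructions manual should say how an increase over that pattern is recognised for scoring.

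The cost is a few words and one baseline item; visits and sample size are unchanged. Comparability with any earlier trial that used the unqualified wording would be slightly less direct. A sensitivity analysis under the unqualified scoring can be produced if the actual support received is also recorded at each assessment.
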